#### 3.2.2 CHILDREN'S ENROLLMENT

The sample will consist of children aged 6-59 months with uncomplicated SAM. In all arms children with severe edema, failing appetite test or having other severe medical complications will be excluded (they will be referred for inpatient treatment). In the arms with CMAM protocol inclusion, criteria will be: bilateral pitting edema (+/++) and/or weight-for-height below -3 Zscore of the World Health Organization Growth Reference and/or MUAC<115mm. In the intervention arm 2, the combined/simplified protocol considers just bilateral pitting edema (+/++) and/or MUAC as only anthropometric admission criteria.

SAM children enrolled in treatment with the CMAM protocol will receive RUTF doses according to their weight (200Kcal/kg/day) whilst those in the combined/simplified protocol will receive a fixed quantity (two sachets RUTF=1000Kcal/day). MAM treatment will be assured in all arms consisting of 500Kcal/day (CMAM: 1 sachet RUSF; Combined/Simplified: 1 sachet RUTF) although MAM children will not be included in analysis. The prevalence of MAM usually triples that of SAM and including MAM data would imply a huge increase in sample size and the need of hiring more supervisors to collect disaggregated data and to keep data quality. This economical overrun couldn't be assumed by the project's budget.

In all arms, discharge criteria will be: absence of edema and reaching the anthropometric cut-off point and maintaining these criteria for two consecutive visits. In CMAM protocol, this depends on the reason for admission (weight-for-height  $\geq$  - 1.5 Zscore or MUAC  $\geq$ 125 mm) and in the combined/simplified protocol it is only MUAC  $\geq$ 125 mm.

#### 3.2.3 DATA COLLECTION AND ANALYSIS

The comparability of the three arms is assumed due to randomization process but even so, it is intended that carers of the children enrolled will complete a short socio-economic survey at admission containing questions related to characteristics of household, livelihoods, hygiene practices and health services utilization according to the Demographic and Health Surveys Program methodology, as well as a Household Dietary Diversity Score. Those socio-economic variables will enable us to describe the sample and they will be used as possible confounders for the adjustment of regressions and risks analysis and to explore which of that has more impact on children's recovery in each arm.

To achieve our objectives, we will consider two main independent variables:

- Treatment provider (HC vs. HC+CHWs)
- Protocol applied in the case of CHWs areas (CMAM vs. Combined/Simplified).

The dependent variables to compare within SAM children (enrolled with MUAC<115mm in the three arms) will be the rates of: recovery (discharge as cured), default (children absent from treatment two consecutive follow-up visits), unresponsiveness (children not improving their nutritional status in two consecutive visits), transfer to inpatient treatment due to health complications and death.

Other variables to be compared will be severity at admission (MUAC measurement and presence of edema), prevalence of non-severe complications at admission and during treatment, treatment length and average daily weight and MUAC gain. Other routine information will be recorded monthly such as referral records and stock supplies.

Disaggregated data on the study subjects will firstly be recorded on paper (patient cards) by HC staff and CHWs according to the specific requirements of the MoH. The data will then be periodically reported by the supervisors via tablet using KOBO software which allows control of transcription errors improving data quality.

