#### 3.2 EFFECTIVENESS ASSESSMENT

#### 3.2.1 SAMPLE SIZE AND CLUSTERING

The sample size was calculated for a binary outcome (recover/not recover) assuming 5% non-inferiority margin, 80% power, 95% sensitivity, a recovery rate of 75% in the control group (as required by SPHERE standards), a recovery rate of 85% in the intervention group (as assumed in the similar ComPAS study described in the introduction section).

The number of clusters required has been calculated according to Hayes and Bennett formula assuming a 0.05 intra cluster correlation coefficient (same as in the ComPAS study). Including 10% loss to follow-up, this resulted in a sample size of 576 SAM children per arm requiring 6 clusters each (96 children per cluster). Therefore, total sample will consist of 1,728 children by country.

Each cluster will correspond to one treatment provider (HC or its group of CHWs) which means that there will be 6 groups of providers by arm. However, in order to avoid final real imbalance in clusters size, the unit of randomization will be the health center with an allocation ratio of 2:1:1. Using this approach, there will be 6 HC allocated to control arm (=6 providers) and 3 HC allocated to each intervention arm with their 3 groups of CHWs (=6 providers). This allocation ratio is based on the figures from our previous studies in Mali were each CHW treated more children on average than each HC during a 12-month period. If all arms involved the same number of HC, the intervention arms would recruit many more children than the control (children from 6 HC plus those of their CHWs).

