#### 5 RESEARCH IMPACT

#### 5.1 EXPECTED RESULTS

This intervention it is expected to contribute to an improvement in access to care during humanitarian crises and a reduction in the number of children dropping out of acute malnutrition management programs. The advantages of this approach are the early diagnosis and care of malnourished children, which could lead to a reduction in the development of medical complications and impact on the health costs for households.

More cost-effective interventions will also allow health authorities to develop strategies for reaching a higher number of malnourished children during crises.

By improving CHW's capacities, and integrating SAM management into the iCCM package, the intervention also aims to have a positive impact on the management of other illnesses with a high mortality rate (diarrhoea, malaria and pneumonia).

The results generated by this research could provide key evidence for the full scale-up of this approach at country-level and in the Sahel region, improving SAM treatment coverage and contributing to a reduction in child mortality, particularly during humanitarian crises.

The specific results expected from the research are:

- 1) Effectiveness of a new intervention model with CHWs
- Evidence on the performance of the SAM care delivered by CHWs: Non-inferiority of the cure rate of children receiving care from the CHWs (greater or equal to the care provided by staff at HC).
- Evidence on the performance of the SAM care delivered using the simplified/combined protocol: Non-inferiority of the cure rate of children receiving care with this protocol.
- Evidence of an increase in the coverage of SAM treatment, in the health areas where treatment is available at HC level and CHW sites.
- 2) Contribution to the continuity of care
- Improvement of the continuum of care for SAM children across all levels of the health pyramid, starting from the Hospital Referral Health Centre (for SAM children with complications), to the HC (for SAM children without complications
   CMAM Approach), through to community-level care delivered by CHWs (for SAM children without complications - iCCM approach).
- 3) Cost-effectiveness of the intervention
- Cost-effectiveness analysis of the different models of SAM treatment: with the hypothesis of sharing the costs already in place for the iCCM intervention, but with an increase in the provision of services including SAM in the Community Primary Healthcare services package.

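### The single 80% power statement does not cover the protocol comparison within CHW areas: with equal recovery, its power is about 7–25% per country

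*Protocol*

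**What the plan says.** Section 3.2.1 contains one calculation for the whole trial, "assuming 5% non-inferiority margin, 80% power, 95% sensitivity", with "a recovery rate of 75% in the control group" and "a recovery rate of 85% in the intervention group". It adds "assuming a 0.05 intra cluster correlation coefficient" and "Including 10% loss to follow-up", and arrives at a "sample size of 576 SAM children per arm requiring 6 clusters each (96 children per cluster"). A cluster is defined there as one provider, six per arm. The same section randomises health centers 2:1:1, so each intervention arm has three randomised centers per country.

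Section 3.2.3 lists two main independent variables: the provider, and "Protocol applied in the case of CHWs areas (CMAM vs. Combined/Simplified". Section 5.1 lists two separate non-inferiority results. The first concerns care by CHWs. The second is "Non-inferiority of the cure rate of children receiving care with this protocol", with no comparator named. The research question in 2.1 asks whether CHWs using the combined/simplified protocol do at least as well as under the current CMAM protocol. Together with 3.2.3, this makes CMAM within CHW areas the most natural comparator.

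**The concern.** The planned power comes largely from the assumed 10-point advantage. The distance from the expected difference to the margin is 5 + 10 = 15 points. Between the two CHW arms the protocol states no advantage. If the single 85% is applied to both, the distance falls to 5 points, and the required number of clusters rises about ninefold before the change in variance. The comparison also rests on three randomised centers per arm.

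A reader of 3.2.1 and 5.1 would take the 80% to apply to both non-inferiority results. Two misreadings could then follow. A wide interval crossing −5 points could be taken as evidence that the simplified protocol is worse. Or a favourable comparison of the combined arm with control could be taken as evidence about the protocol, although those arms differ in provider as well. Sections 5.1 and 5.2 direct these results at scale-up and national policy.

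**Working it through.** **Inputs.** From 3.2.1: margin 0.05, recovery 0.75 and 0.85, ICC 0.05, 10% loss, 6 × 96 children per arm. Evaluable children are 0.9 × 96 = 86.4 per provider, 172.8 per health center and 518.4 per arm. The 95% sensitivity is read as the confidence level. Sidedness is not stated, so one-sided 2.5% and 5% are both shown. Applying the ICC of 0.05 at health-center level is an assumption.

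**Step 1: the plan's own figure.** Clusters per arm:

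c = (z_α + z_β)² × [p₀(1−p₀) + p₁(1−p₁)] × [1 + (m−1)ρ] / [m × (margin + p₁ − p₀)²]

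The variance term is 0.1875 + 0.1275 = 0.315, the design effect is 1 + 85.4 × 0.05 = 5.27, and the distance is 0.15.

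- One-sided 5%: 6.18 × 0.315 × 5.27 / (86.4 × 0.0225) = 5.28, which rounds up to 6. Adding the extra cluster of the Hayes–Bennett formula gives 6.28.
- One-sided 2.5%: the factor is 7.85 and c = 6.70, or 7.70 with the extra cluster.
- Power with 6 v 6: SE = √(0.315 × 5.27 / 518.4) = 0.0566 and 0.15/0.0566 = 2.65. This gives 79% (t, 10 df) to 84% (normal) at one-sided 5%, and 67–76% at 2.5%.

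So 6 × 96 at 80% is consistent with one-sided 5% and provider clusters, but not with one-sided 2.5%.

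**Step 2: CMAM versus combined within CHW areas, equal recovery.** The distance is 0.05. At 85% in both arms the variance term is 0.255.

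- 3 v 3 health centers: design effect 1 + 171.8 × 0.05 = 9.59; SE = √(0.255 × 9.59 / 518.4) = 0.0687; 0.05/0.0687 = 0.73.
- 6 v 6 providers: SE = √(0.255 × 5.27 / 518.4) = 0.0509; 0.05/0.0509 = 0.98.

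Power per country (noncentral t to normal approximation):

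| Clusters | Alpha, one-sided | Both 85% | Both 75% | 75% v 85% |
|---|---|---|---|---|
| 3 v 3 health centers | 2.5% | 8–11% | 7–9% | 33–50% |
| 3 v 3 health centers | 5% | 15–18% | 13–15% | 49–63% |
| 6 v 6 providers | 2.5% | 14–16% | 11–13% | 67–76% |
| 6 v 6 providers | 5% | 23–25% | 19–20% | 79–84% |

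The last column assumes that the combined protocol is 10 points better than CMAM within CHW areas.

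**Step 3: both countries pooled, both arms at 85%.** With 6 v 6 health centers, power is 15–18% (one-sided 2.5%) or 25–27% (5%). With 12 v 12 providers it is 26–28% or 38–40%.

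**Step 4: size needed.** For 80% power per country at equal 85% with provider clusters, c = 6.18 × 0.255 × 5.27 / (86.4 × 0.0025) = 38.5 per arm at one-sided 5%. At 2.5% it is 48.8. The plan has 6.

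**Step 5: sensitivity.** With 94.2% recovery in both arms (the CHW cure rate of the earlier Mali study quoted in 1.1), power per country is 14–20% (3 v 3) or 27–32% (6 v 6) at one-sided 2.5%, and 24–30% or 40–44% at 5%. With an assumed ICC of 0.01 and both arms at 85%, it is 19–28% (3 v 3) or 32–38% (6 v 6) at 2.5%.

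**The case against.** The strongest reply concerns the 85%. Section 3.2.1 takes it from ComPAS, which 1.1 presents as similar work on integrated SAM and MAM care, so 75% v 85% could be read as an assumption about CMAM versus the combined protocol. On that reading, with 6 v 6 providers and one-sided 5%, the second comparison has 79–84% power. This has some force: equal rates in the two CHW arms are an inference from a single intervention figure. But 3.2.1 labels the two rates control and intervention, and both CHW arms are intervention arms. At the randomised unit, even this reading gives only 33–63%.

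Also fair: 5.1 names no comparator, and the cost-effectiveness and coverage sections compare intervention arms with control. Sections 2.1 and 3.2.3 still favour the comparison within CHW areas. The combined arm against control would change provider and protocol together.

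Four stronger readings are tempting, and the protocol does not support them:

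- That power is simply 8–11%. This needs one-sided 2.5%, health-center clusters and equal 85%; the plan's alpha is not stated, its clusters are providers, and its size fits one-sided 5%.
- That failure to show non-inferiority is near certain. At equal 85% it is about 75–92% per country and 60–85% pooled.
- That the third specific objective cannot be answered. It asks whether CHWs can use the combined protocol effectively, which estimation can address.
- That an exact randomisation test on 3 v 3 centers could not reach significance. No such test is planned, and its smallest p-value, 1/20 = 0.05, meets a one-sided 5% threshold.

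**Conclusion.** The concern holds in this form: the protocol gives one power figure, and it does not carry over to the second of its two main comparisons unless a further 10-point advantage is assumed there. With equal recovery of 75–85%, ICC 0.05 and 10% loss, power is about 7–25% per country; pooled at equal 85%, it is about 15–40%. The spread reflects what 3.2.1 leaves open (alpha and sidedness) and whether provider or randomised center is the cluster. Higher recovery or a lower ICC raises the figures, but no equal-recovery case examined reaches 80% per country.

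At equal 85% with three centers per arm, the 95% interval has a half-width of about 2.776 × 0.0687 = 19 points per country. An interval that wide cannot separate a 5-point loss from no loss, so a failed test would say little about the protocol.

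**What to change.** In 3.2.1, state the alpha and its sidedness. Say that the 80% applies only to intervention versus control under 75% v 85%. Give the power of the protocol comparison within CHW areas under equal recovery, with the randomised health center as the unit. If a 10-point advantage of the combined protocol over CMAM was intended, say so and justify it.

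In 5.1, name the comparator for the second non-inferiority result. Report that comparison as a difference with its confidence interval, both countries combined and stratified by country. Claim non-inferiority of the protocol only if the interval lies above −5 points, and state that failure to show it is not evidence of inferiority. Label the combined arm versus control as a package effect of provider plus protocol.

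The cost is a less favourable stated power. No extra children are needed. The changes do not raise the power; they align the claims with what the design can show.

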Evidence on the effectiveness of CHWs treating SAM has been summarized in a recent review published by our team^8. It included nine operational experiences in non-emergency contexts. Most reach 90% cure rates with default and death rates below 7% and 1.5% respectively. These results are even better than those from facility-based programmes, having the potential for early detection and thereby preventing complications. Coverage assessments were conducted in three studies, reaching 80% and cost-effectiveness was demonstrated in the two programmes which assessed it (compared with inpatient and CMAM). However, no evidence has been found on CHWs treating SAM in emergency settings.

Current evidence on the integration of SAM and MAM into the same protocol is scarce. There is one example in Angola achieving 93.8% recovery. In addition, another study at health facility-level in post-conflict Sierra Leone shows that integrating care for SAM and MAM allows reaching a 71% treatment coverage and

83% recovery for GAM (versus 55% and 79% respectively in the standard care applying two different protocols). SAM children receiving integrated management recovered faster, resulting in lower spend on RUTF (\$36 vs. \$68) whilst the cost for MAM was equal (\$12). Authors recommended this model as an alternative in humanitarian crises where time is essential since it reduces logistics complexity and is easy to deliver based on MUAC-only criteria. Another similar study ('ComPAS') is currently being implemented in South Sudan and Kenya but results are not yet available.

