- Evidence on the reduction of costs for household and of treatment duration. We are seeking to remove barriers (such as geographical access and economic obstacles) to the provision of care in a humanitarian crisis context.

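### The proportion of children with non-severe complications during treatment depends on how long each child is observed, and the plan expects treatment length to differ between arms

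*Protocol*

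**What the plan says.** Protocol section 3.2.3 names, among the further variables to be compared, "prevalence of non-severe complications at admission and during treatment, treatment length and average daily weight and MUAC gain". Treatment length is a separate variable in the same list. No time-at-risk denominator and no window common to the arms is attached to the complications variable.

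Treatment has no fixed length. Under section 3.2.2 a child is discharged on "absence of edema and reaching the anthropometric cut-off point and maintaining these criteria for two consecutive visits". For the anthropometric cut-off the section says "In CMAM protocol, this depends on the reason for admission" (weight-for-height of at least -1.5 Z or MUAC of at least 125 mm), whereas "in the combined/simplified protocol it is only MUAC" of at least 125 mm. Section 3.2.3 adds default, transfer and death as other ways out. Section 3.1 gives a calendar period for recruitment and follow-up, but no follow-up length per child.

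On expectations, section 5.1 lists "Evidence on the reduction of costs for household and of treatment duration" among the results sought, and section 1.1 reports from a facility-level study that "SAM children receiving integrated management recovered faster, resulting in lower spend on RUTF". Section 5.1 also says that early diagnosis and care "could lead to a reduction in the development of medical complications".

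**The concern.** A proportion of children ever ill during a period grows with the length of the period. If children in one arm leave treatment sooner, fewer of them will have a complication recorded even when their weekly risk is the same. The comparison as listed cannot separate fewer illnesses per week from fewer weeks observed.

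At stake is a secondary conclusion: whether a model of care is accompanied by fewer non-severe complications. Recovery, the sample size and the non-inferiority test do not depend on it.

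**Working it through.** **Nothing to reproduce.** The protocol gives no figure for complication frequency or treatment length. What follows illustrates the mechanism; the 6-week control window and the control prevalences of 10% to 40% are assumptions.

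**Step 1: same risk, different window.** Let the weekly risk of a first complication be constant and equal in two arms. If a proportion p is ever ill over a window T0, the proportion recorded over a window T1 is

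P(T1) = 1 - (1 - p)^(T1/T0).

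With T0 = 6 weeks and p = 20%:

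- T1 = 5 weeks: 1 - 0.80^(5/6) = 17.0%, ratio 0.85.
- T1 = 4 weeks: 1 - 0.80^(4/6) = 13.8%, ratio 0.69.

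Across the assumed range (recorded proportion, with its ratio to the 6-week value):

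| Ever ill at 6 weeks | 5.4 weeks | 5 weeks | 4 weeks |
|---|---|---|---|
| 10% | 9.0% (0.905) | 8.4% (0.841) | 6.8% (0.678) |
| 20% | 18.2% (0.910) | 17.0% (0.848) | 13.8% (0.691) |
| 30% | 27.5% (0.915) | 25.7% (0.857) | 21.2% (0.705) |
| 40% | 36.9% (0.921) | 34.7% (0.867) | 28.9% (0.722) |

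The relative shortfall is close to the relative cut in treatment length, and somewhat smaller when complications are common. Scaled to the planned 576 children per arm (section 3.2.1), the 20% row gives about 115 children at 6 weeks against about 98 at 5 weeks or 80 at 4 weeks, with no true difference.

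**Step 2: does lower default cancel it?** Default also ends observation, and section 5.1 expects less of it. The earlier Mali study cited in section 1.1 had default of 4.5% with CHWs against 10.8%, a difference of 6.3 points. If defaulters leave halfway through 6 weeks (assumed), the gain in mean observation is 0.063 x 3 = 0.19 weeks, and 0.19/6 is about 3%. That would not cancel a cut of 10% or more.

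**Step 3: does a rate per child-week solve it?** Under constant risk, yes: the rate ratio is 1.00 at every window length. If illness instead clusters soon after admission, the rate errs the other way. When both arms have the same events in the same early weeks but windows of 5 and 6 weeks, the shorter arm's rate is 6/5 = 1.20 times the other's with no true difference. Neither measure is safe alone.

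**Step 4: where would unequal windows come from?** Control and the CHW arm using CMAM share one discharge rule. Section 3.2.3 restricts the main outcome comparison to children enrolled with MUAC below 115 mm, and for them MUAC of at least 125 mm is largely the exit criterion in all three arms. What remains is speed of recovery, default, transfer and death.

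**The case against.** The strongest case on the other side has five parts.

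- *The discharge rules hardly differ for the children compared.* This stands. A reader might infer from the two rules in section 3.2.2 that the arms have unequal observation windows by design. The MUAC restriction and the rule shared by the two CMAM arms do not support that. Some ambiguity remains for children in the CMAM arms who meet both admission criteria, and over whether the restriction extends to the further variables.
- *Shorter treatment is only weakly supported, and no direction is fixed.* This largely stands. The line in section 5.1 is one item under cost-effectiveness, with no arm and no size. The faster recovery in section 1.1 comes from integrated care at health facilities, not from CHW delivery. The rations in section 3.2.2 also differ by protocol (1000 kcal/day fixed, 200 kcal/kg/day by weight, equal at 5 kg), so the text does not settle which protocol gives the shorter treatment.
- *The comparison is not shown to favour the hoped-for result.* A reader might infer that it is, because section 5.1 expects an approach "which could lead to a reduction in the development of medical complications and impact on the health costs for households". That sentence concerns medical complications avoided through early diagnosis and care. The variable here is non-severe complications, and transfers for health complications are a separate outcome. The documents do not tie the two together.
- *Complications per treatment episode is a legitimate quantity.* True. If a model cures sooner, fewer illnesses during treatment may be part of its benefit. This is a reason to keep the proportion, not to leave it unaccompanied.
- *The summary measure belongs in the SAP, and prevalence could mean a proportion of visits.* The SAP is not shown and may address this; its absence is not the point. The protocol itself names the measure, and on its ordinary reading that measure depends on the window. A per-visit proportion would be less affected, but the text does not say that is meant.

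**Conclusion.** The point holds in a limited form. Section 3.2.3 fixes a between-arm comparison whose value depends on how long each child is observed, observation stops when treatment stops, and the plan expects treatment length to change. A difference in the proportion ever ill during treatment can therefore partly reflect weeks observed.

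The size and direction cannot be derived from the documents. The illustrative ratios of 0.84 to 0.87 (5 of 6 weeks) and 0.68 to 0.72 (4 of 6 weeks) rest on an assumed control window, assumed prevalences of 10% to 40%, and a constant risk equal in both arms. If risk is concentrated early, the artefact in the proportion is smaller. Prevalence at admission and the primary recovery comparison are unaffected. This is a minor improvement to a secondary variable.

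**What to change.** In section 3.2.3, keep the proportion with a complication during treatment and keep the admission prevalence. Add a comparison of new complications per child-week of treatment, broken down by week since admission, or limited to the same early weeks in all arms. The breakdown prevents early clustering of illness from making the shorter-treated arm look worse. State that a claim of fewer complications will be made only if the proportion and the time-adjusted measure agree. If only the proportion is lower, report fewer illnesses per treatment episode and do not infer a lower risk of illness. State also whether prevalence is counted per child or per visit.

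The cost is a little more analysis, using treatment length that is already to be collected. There is one condition: new complications must be recorded by visit on the patient card. The protocol says individual data go on the cards as the Ministry of Health requires, but does not say that complications are dated. This should be confirmed, and if necessary a field added, before enrolment.
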